12 biofeedback (n=164). Inclusion criteria include: adults with a current episode of LBP >3
13 months; sought primary care ≥ 6 weeks ago for this episode of LBP; average LBP intensity of
14 ≥ 4 (0-10 scale); at least moderate pain-related interference with work or daily activities. The
15 CFT only and CFT-plus-movement-sensor-biofeedback participants will receive seven
16 treatment sessions over 12 weeks plus a 'booster' session at 26 weeks. All participants will be
17 assessed at baseline, 3, 6, 13, 26, 40 and 52 weeks. The primary outcome is pain-related
18 physical activity limitation (Roland Morris Disability Questionnaire). Linear mixed models
19 will be used to assess the effect of treatment on physical activity limitation across all time
20 points, with the primary comparison being a formal test of adjusted mean differences between
21 groups at 13 weeks. For the economic (cost-utility) analysis, the primary outcome of clinical
22 effect will be quality-adjusted life years measured across the 12-month follow up using the
23 EQ-5D-5L.

1
2
3 1 Ethics and dissemination: Approved by Curtin University Human Research Ethics Committee
4
5 2 (HRE2018-0062, 6th Feb 2018). Study findings will be disseminated through publication in
6
7 3 peer-reviewed journals and conference presentations.
8
9

10 4 Trial Registration: Australian and New Zealand Clinical Trials Register:
11
12 5 ACTRN12618001396213
13
14
15 6
16 7
17
18

19 8 **Strengths and limitations of this study:**

- 20
21 9 • The first fully powered study comparing Cognitive Functional Therapy to usual care as
22
23 10 control
24
25 11 • Three-arm trial to quantify the added contribution of movement sensor biofeedback to
26
27 12 Cognitive Functional Therapy
28
29 13 • Evaluation of whether cognitive or movement changes mediate improvements
30
31 14 • Evaluation of economic efficiency in addition to clinical effectiveness
32
33 15 • Full participant and therapist blinding not possible
34
35
36
37 16
38
39 17
40
41

42 18 **Keywords**

43
44 19 Low back pain, wearable electronic devices, rehabilitation, clinical trial protocol
45
46
47
48
49
50
51
52
53
54
55
56
57
58
59
60

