15 University Human Research Ethics Committee approved the study (HRE2018-0062, 6
16 February 2018) and the trial is registered with the Australian and New Zealand Clinical Trials
17 Registry (ACTRN12618001396213). The protocol follows the SPIRIT recommendations²¹.

18

19

20 **Participants**

21 We will recruit 492 adult participants who meet these inclusion criteria: a current episode of
22 non-specific LBP lasting more than 3 months (including cases with leg pain); presenting to a
23 primary care clinician at least 6 weeks ago for this episode of LBP; scoring an average LBP
24 intensity of 4 or more on a 0-10 Numerical Rating Scale²²; and having at least moderate pain-
25 related interference with normal work or daily activities (measured by item 8 of the SF-36)²³.

26 Patients will be excluded if they have any diagnosed medical conditions that prevent them

27

1 from being physically active; have a serious spinal pathology (e.g. fracture, infection,
2 cancer); are pregnant or have given birth within the previous 3 months; have inadequate
3 English to comprehend the study's questionnaires and instructions; have a skin allergy to
4 hypoallergenic band-aid or tape adhesives; or are scheduled for major surgery in the next 3
5 months. In addition to those inclusion criteria, participants will be informed of the locations
6 of the physiotherapy clinics for the study intervention groups and will only be included in the
7 trial if they are willing to travel for treatment to at least one site delivering either of the
8 possible interventions.

9 Patient and public involvement

10 Patients and the Public were not directly involved in the design, recruitment to or conduct of
11 this study. They will be involved in our plans to disseminate the study results to participants
12 and relevant community groups, by assisting in the choice of what information/results to
13 share, and in what format.

14 **Recruitment**

15 Trial participants will be recruited via clinicians (e.g. GPs, physiotherapists, pain clinics,
16 surgeons), or directly from the community (e.g. via print media and social media). Clinicians
17 will conduct a preliminary screening of patients with LBP and inform potential trial
18 participants about the study. Those patients who request further information about the study
19 will be provided with a flyer, which directs them to the study website
20 (<https://www.restorebackpain.com/>) where greater study details, including the participant

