24 the patient nor the clinician will have access to it (only the researchers have access). The
25 ViMove2 device (DorsaVi P/L, Melbourne, Australia) consists of miniaturised sensors

1 attached to the lumbar spine with hypoallergenic tape, and communicate wirelessly with a
2 tablet or mobile phone (Figure 2). At all treatment sessions, patients in both CFT groups will
3 perform forward bending in standing and two other clinically-relevant functional movements
4 selected by the physiotherapist based in the patient specific functional scale. All three
5 movements will be repeated three times and data recorded via the movement sensors.

6 7 *Differences across the two CFT treatment groups*

8 *Group 2: Cognitive Functional Therapy only (CFT-only)*

9 Clinicians and patients in this group will be blinded to all movement sensor output by a
10 software block that only allows the sensors to be configured/started and for the data to be
11 automatically uploaded to a secure cloud-based server. Participants will be told the device is
12 being used to collect outcome data.

13 14 *Group 3: CFT-plus-movement-sensor assessment and biofeedback (CFT-plus-movement- 15 sensor-biofeedback)*

16 Clinicians in this group will treat patients with the same CFT approach as in the CFT-only
17 group except that in addition, these clinicians will have access to data measured by the
18 movement sensors and be able to use these data for assessment, movement retraining and
19 providing biofeedback. The identification of clinically relevant functional movement
20 behaviors in this particular treatment group will also be informed by data from the movement
21 sensors that are graphically analysed and displayed by the ViMove2 software (Figure 3).

22
23 This additional information could assist in guiding individualised movement retraining
24 incorporating the following strategies. Firstly, ‘live assessment’ can assist in identifying
25 unusual kinematic parameters or movement patterns.²⁶ Secondly, ‘live training’ in the clinic,

1 allows visual interaction by observing real-time kinematic and EMG on-screen data to
2 facilitate changing functional movement behaviours. Thirdly, using the ViMove2 software,
3 clinicians can program movement sensor biofeedback alerts (audio ‘beeps’ and messages via
4 a trial-supplied iPhone) that will reinforce key principles from the treatment session while the
5 participant goes about their normal daily activities for the rest of the day. The device will

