- 2 • Pain catastrophisation (Pain Catastrophizing Scale)³³
- 3 • Pain self-efficacy (Pain Self-efficacy Questionnaire)³⁴
- 4 • Fear of movement (physical activity subscale of the Fear Avoidance Beliefs Questionnaire)³⁵
- 6 • Patient-perceived global improvement (1 question)³⁶
- 7 • Patient satisfaction with care and treatment (1 question)³⁷
- 8 • Adverse events (defined as any morbidity or events causing unwarranted distress to a participant that were potentially related to any trial-related intervention). Clinicians and follow-up questionnaires will inquire about any adverse events.
- 11 • Lumbosacral movement will be measured in both CFT treatment groups using ViMove2 wearable wireless sensors and used in the mediation analysis.
- 13 • Direct health costs attributable to consumption of health care resources (measured using extracts from Medicare and Pharmaceutical Benefits databases and direct patient reports) and productivity costs (measured using the iMTA Productivity Cost Questionnaire³⁸).

17 **Sample size calculation**

18 The sample size was calculated for the primary outcome using the program STATA. A total
19 of 492 patients (164 per group) will be recruited to detect a difference of 2 points (0-24 scale)
20 on the RMDQ between the CFT-only group and CFT-plus-movement-sensor-biofeedback
21 group, $p < 0.05$, 80% power, a common standard deviation of 6 points and a worst-case
22 scenario of 20% drop-out rate. Based on our pilot study results^{20 39}, we hypothesise that the
23 CFT-plus-movement-sensor-biofeedback group would have an average score of 7.5 points on
24 the RMDQ and the Usual care group would have a score of 11.5 points. Pragmatically and
25 arbitrarily, we assume the CFT-only group will have a mean outcome that is half-way (9.5)

1 between the other two groups and so we will power the trial to detect this as the smallest
2 likely between-group difference ($11.5-9.5=2.0$).

4 **Blinding**

5 Patients will not be informed of any anticipated results of the trial and will be told that the
6 trial is comparing usual care to two evidence-based interventions. All outcome measures will
7 be either self-reported by patients via web-based questionnaires or collected via the
8 movement sensors or MBS/PBS registers. Unblinded clinicians will deliver only type of one
9 treatment and play no role in collecting data, other than performing a standardised movement

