10 protocol with the resultant movement data being automatically uploaded by the sensors to a
11 server without clinician input. Statisticians will be blind to groups.

13 **Statistical analysis**

14 Almost all participant-reported data will be entered directly into an electronic database,
15 where range values are automatically checked. In addition, all data will be checked for range
16 values and outliers prior to analysis.

18 *Treatment efficacy analysis*

19 Repeated-measure linear mixed models will be used to assess the effect of treatment on pain-
20 related physical activity limitation across all time points (3, 6, 13, 26, 40 and 52 weeks), with
21 the primary comparison being a formal test of adjusted mean differences between groups at
22 13 weeks using intention-to-treat principles. Appropriate sensitivity analyses will be
23 performed on multiple imputed datasets. Estimates of treatment effect will be adjusted for
24 baseline scores of symptom duration, pain intensity, activity limitation (RMDQ score),
25 treatment expectations and significant clinician cluster effects.

1
2
3 1 The secondary outcome measures will be evaluated using the equivalent repeated-measure
4
5 2 linear mixed models.
6
7
8 3

9
10 4 As widely recommended, we will focus on reporting the size of the effect and its uncertainty
11
12 5 (including describing compatibility intervals and p-values) rather than making judgements
13
14 6 based on an arbitrary p-value threshold⁴⁰⁻⁴². In the papers that report the outcomes of this
15
16 7 clinical trial, effect sizes will be discussed relative to those obtained by other interventions in
17
18 8 comparable populations.
19
20
21 9

22 23 24 10 *Analysis of economic efficiency*

25
26 11 Direct healthcare and indirect (productivity) costs incurred by participants will be measured
27
28 12 over the 12-month follow-up period. Direct health costs will be collected using Medicare
29
30 13 Benefits Scheme (MBS) and Pharmaceutical Benefits Scheme (PBS) database extractions,
31
32 14 and patient questionnaires to capture other health care costs (e.g. hospitalisations). Indirect
33
34 15 health costs (e.g. travel to appointments) and productivity costs (including absenteeism and
35
36 16 presenteeism) will also be captured in the 3-monthly patient questionnaires. Productivity
37
38 17 costs will be measured using the 'iMTA Productivity Cost Questionnaire'. Productivity costs
39

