
Version 1, 12 April 2019

Table 1: Trial data collected and their purpose

Construct	Measure	Time points (weeks)	Purpose
Age	Date of birth	0	Describe population
Sex	Male/Female	0	Describe population
Duration of episode	Weeks	0	Describe population
Duration since care-seeking	Weeks	0	Describe population
Previous lifetime episodes	Number	0	Describe population
Height	Centimeters	0	Describe population
Weight	Kilograms	0	Describe population
Education	Categorical	0	Describe population
Current role	Categorical	0	Describe population
Employed	Yes/No	0	Describe population and analysis of economic efficiency
Occupation	Open text	0	Describe population and analysis of economic efficiency
Hours working	Hours	0	Describe population and analysis of economic efficiency
Days working	Days	0	Describe population and analysis of economic efficiency
Sick leave last 3/12	Yes/No	0, 12, 26, 40 and 52	Describe population and analysis of economic efficiency
Days of sick leave 3/12	Days	0, 12, 26, 40 and 52	Describe population and analysis of economic efficiency
Pain-related physical activity limitation	Roland Morris Disability Questionnaire ⁴⁷	0, 3, 6, 12, 26, 40 and 52	Describe population, primary outcome, analysis of economic efficiency

Functional limitation	Patient-Specific Functional Scale ⁴⁸	0, 3, 6, 12, 26, 40 and 52	Secondary outcome
Pain intensity	Numeric Pain Rating Scales ³¹	0, 3, 6, 12, 26, 40 and 52	Describe population, secondary outcome
Fear avoidance beliefs	Fear Avoidance Beliefs Questionnaire (physical activity sub-scale) ³⁵	0, 12, 26, 40 and 52	Describe population, secondary outcome, mediator
Analgaesic use	Participant self-report text box	0	Describe population, secondary outcome (when matched to 12-month Pharmaceutical Benefits Scheme data)
Catastrophising	Pain Catastrophizing Scale ³³	0, 3, 6, 12, 26, 40 and 52	Describe population, secondary outcome, mediator and moderator
Pain self-efficacy	Pain Self-efficacy Questionnaire ³⁴	0, 3, 6, 13, 26, 40 and 52	Describe population, secondary outcome, mediator and moderator
Quality-adjusted life years	EuroQOL EQ-5D-5L ⁴⁹	0, 12, 26, 40 and 52	Analysis of economic efficiency outcome
Treatment expectations	A tailored question, based on Rofail, Myers and Froggatt 2016 ⁵⁰	0 (post-randomisation)	Clinical effectiveness baseline covariate
Confidence in intervention	A tailored question, based on Rofail, Myers and Froggatt 2016 ⁵⁰	3 (CFT groups only)	Mediator
Cognitive flexibility	Cognitive Flexibility Inventory ⁵¹	0	Moderator

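### The description given to participants calls both CFT arms evidence-based and leaves usual care unlabelled, which may add expectation bias to the two unblinded CFT-versus-usual-care contrasts

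*Supplement*

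**What the plan says.** One sentence in the Blinding section both withholds and supplies information. It reads "Patients will not be informed of any anticipated results of the trial and will be told that the" "trial is comparing usual care to two evidence-based interventions". The same section says outcomes will "be either self-reported by patients via web-based questionnaires or collected via the" movement sensors or the health-service registers. The RMDQ is one of the questionnaires.

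Other places that bear on the point:

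- **Strengths and limitations** concedes: "Full participant and therapist blinding not possible".
- **Group 2 (CFT-only)** describes masking by sensors whose output is blocked. Its sentence beginning "Participants will be told the device is" goes on to say that the sensors gather outcome data. Usual care has no counterpart.
- **Participants** admits only people prepared to travel to a clinic delivering one of the interventions.
- **Treatment efficacy analysis** adjusts the primary estimate for, among other things, "treatment expectations and significant clinician cluster effects".
- **Table 1** lists the expectation item as a baseline covariate, but its time-point entry begins "0 (post-randomisation".

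**The concern.** Withholding anticipated results is meant to keep expectation even across arms. Describing two arms as evidence-based and leaving the third without a description works against that aim. A participant allocated to usual care can infer that they missed the two options with evidence behind them, and a participant allocated to CFT can infer that they received one.

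This matters because the main defence against such effects, masking, is absent where it is most needed. Disability, pain, global improvement, satisfaction and the EQ-5D-5L behind the QALYs all come from people who know whether they are having CFT. If the wording lifts expectation in two arms and lowers it in the third, part of the 13-week difference from usual care could reflect reporting rather than treatment. Unlike open-label delivery, the wording can be changed.

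**Working it through.** The plan gives no figure for an expectation effect, so there is nothing to reproduce. The check is mainly a comparison of passages, with one illustration of scale.

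**Step 1: which contrasts are exposed?**

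| Contrast | Label the same in both arms? | Masking described? |
|---|---|---|
| CFT-only v usual care | No | None |
| CFT-plus-biofeedback v usual care | No | None |
| CFT-only v CFT-plus-biofeedback | Yes | Partial (blocked sensors) |

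The asymmetry therefore bears on the first two contrasts and should bear less on the third.

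**Step 2: does the analysis remove it?** The primary model includes treatment expectations. For this to act as an ordinary baseline adjustment, the item must be answered before allocation can influence it. Table 1 puts it after randomisation. The documents do not say whether participants know their arm when they answer. If they do, both the arm and the label may already have shaped the answer. Conditioning on it would then change what is being estimated, and it still would not correct biased reporting of the RMDQ. The only sensitivity analyses named use multiply imputed data, which address missing values and not reporting bias.

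**Step 3: scale, by assumption only.** Inputs from Sample size calculation, taken as stated: SD 6; target difference 2 points; 164 per group; 20% drop-out, so 164 × 0.8 = 131 per group. Suppose there is no true effect and a spurious shift b in favour of CFT. The range of b, 0 to 1 point, is my assumption.

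SE = 6 × √(2/n), which is 0.741 for n = 131 and 0.663 for n = 164.

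Two-sided rejection rate = Φ(−1.96 − b/SE) + 1 − Φ(1.96 − b/SE).

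Example: b = 0.5 and n = 131 give b/SE = 0.675 and a rate of 0.0042 + 0.0993 = 0.1035.

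| b (RMDQ points) | Share of 2-point target | Rate, n = 131 | Rate, n = 164 |
|---|---|---|---|
| 0 | 0% | 5.0% | 5.0% |
| 0.25 | 12.5% | 6.3% | 6.7% |
| 0.5 | 25% | 10.4% | 11.7% |
| 1.0 | 50% | 27.1% | 32.6% |

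The 2-point denominator applies to CFT-only versus usual care (11.5 − 9.5). For CFT-plus-biofeedback versus usual care the protocol anticipates 11.5 − 7.5 = 4 points, so shifts of 0.5 and 1 point are 12.5% and 25% of the expected difference. The calculation ignores baseline adjustment and clinician clustering. It shows what a shift of a given size would do, not how large the shift is.

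**The case against.** The case on the other side is substantial.

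- **The wording states no result.** A reader might infer that it tells participants which arm should win. The documents do not support that: anticipated results are expressly withheld, calling something evidence-based does not say it beats usual care, and usual care is not called unsupported. The Introduction also gives the label some basis, citing a randomised trial of CFT (N=121) and a pilot randomised trial of sensor-biofeedback rehabilitation (N=112). This stands. What remains is an uneven description, not a disclosed result.
- **Withholding results is not the only protection.** The expectation covariate is a planned adjustment. This stands too, but its timing makes it weak protection.
- **Most of the exposure comes from the open-label design.** Entry requires willingness to travel for CFT, so disappointment on allocation to usual care would arise under neutral wording as well, and incomplete blinding is disclosed. This stands. Only the extra contribution of the label is at issue, and it cannot be separated out from the documents.
- **Drop-out and care-seeking.** One might expect the label to drive losses or extra care in usual care. The protocol pays that arm alone for follow-up (AU$30 + $30 + $50 = $110 for completing everything), which works against losses, and it leaves that arm's care unrestricted by design. Neither effect is shown.
- **The wording participants actually read is not shown.** The information sheet and consent form are not among the pages available, so the Blinding section is the only evidence of it.

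None of this removes the asymmetry in the stated script.

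**Conclusion.** The concern holds as a risk. The stated description favours both CFT arms, participants are not masked to CFT versus usual care, and the primary outcome is self-reported. The wording may therefore add to expectation and disappointment effects in the two CFT-versus-usual-care contrasts, most plausibly in CFT's favour, and less so in the contrast between the CFT arms. The planned expectation adjustment does not reliably remove it.

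The size is unknown. The illustrative shifts above rest wholly on an assumed range and cannot be attributed to the label as distinct from open-label delivery. A reader might go further and conclude that the primary contrast is biased, or biased by a given amount. The documents do not support that. The conclusion assumes that participants receive the description as the Blinding section states it.

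**What to change.** For everyone enrolled from the amendment date, replace the description in the Blinding section, and any participant-facing material that repeats it, with a neutral and symmetric one. For example: the trial compares three ways of managing back pain, and it is not known which works best. No arm should be called evidence-based.

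The cost is a small ethics amendment. Recruitment began on 23 October 2018, so people already enrolled will have been given the present description. Record the date of the change and state this as a limitation in the report.

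A comparison of the 13-week contrast before and after the change should not be planned. It would be non-randomised and confounded with calendar time, so it could not show whether the wording mattered.

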8 people to: 1) reconceptualise their pain from a biopsychosocial perspective, while dispelling
9 unhelpful beliefs and identifying new cognitive and behavioral responses to pain, 2) build
10 confidence to engage in functional activities related to their goals through functional
11 movement training and 3) adopt a healthy lifestyle by targeting activity avoidance, poor sleep
12 habits, stress management and dietary advice.¹⁷ A Norwegian study of patients with chronic
13 LBP (N=121), found CFT resulted in large sustained effect sizes (12-month standardised
14 effect sizes from 0.7 to 0.9) compared with guideline-recommended manual therapy and
15 exercise.¹⁸ These findings suggest a large, high quality study is now required.

16
17 With advances in technology, movement sensors enable accurate measurement and
18 monitoring of lumbar spine movements outside the research laboratory¹⁹. Wearable
19 movement sensors enable clinicians to precisely measure movement patterns, postures
20 (functional movements) and their relationship to pain, both in the clinical setting but more
21 importantly, during patients' normal activities (work, rest and play) outside the clinic. In
22 addition, movement sensors could help patients to develop an awareness of how they move
23 and the postures they use during normal activities, where changes to these habituated
24 functional movement behaviors are most important. This technology has the potential to
25 increase the effectiveness of therapies aimed at correcting functional movement behaviours.

1 A recent pilot RCT (N=112) of patients with chronic LBP showed that individualised
2 rehabilitation, based on addressing functional movement behaviours, combined with
3 biofeedback from wearing wireless movement sensors, resulted in large and sustained clinical
4 improvements compared with guideline-recommended treatment (12-month effect sizes from
5 0.5 to 1.0).²⁰

6
7 Therefore, this three-arm RCT aims to compare the clinical effectiveness and economic
8 efficiency of individualised CFT, delivered with or without movement sensor biofeedback,
9 with usual care for patients with chronic, disabling LBP.

10

11 **METHODS AND ANALYSIS**

12 The RESTORE study is a pragmatic, three-arm, parallel group, superiority RCT comparing
13 usual care with CFT only and CFT-plus-movement-sensor-biofeedback in patients with
14 chronic LBP (Figure 1). The trial will be conducted in Perth and Sydney, Australia. Curtin

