6 including patient demographics and outcome measures, via the online database. A researcher
7 will be available by phone if they require assistance. A detailed description of the baseline
8 variables is provided in Table 1.

9 10 **Randomisation**

11 After completing the baseline assessment, dynamic (adaptive) random allocation will be used
12 to randomise participants to treatment groups. Randomisation using a 1:1:1 allocation ratio
13 will be conducted by a research assistant by phoning the NHMRC Clinical Trials Centre (24-
14 hour phone service), thereby ensuring concealment of treatment allocation. The NHMRC
15 Clinical Trials Centre will be blinded to baseline assessment. After randomisation and only
16 for those randomised to the CFT-only and CFT-plus-movement-sensor-biofeedback groups, a
17 research assistant will make an appointment for them with a study clinician at an accessible
18 location in their city.

19 20 **Study treatment**

21 *Group 1: Usual care*

22 This treatment will be the usual care pathway the participant's health providers recommend
23 and/or the participant chooses. Treatment in this group will not be impacted in any way by
24 participation in the study. Participants in this group only will be paid a token reimbursement
25 for their time completing follow-up questionnaires (AU\$30 for the 3-month questionnaire,

1 \$30 for the 12-month questionnaire and an additional \$50 if they complete all the six follow-
2 up questionnaires (3 and 6 week, 3, 6, 9 and 12 month).

3 4 *Commonalities across the two CFT treatment groups (Groups 2 and 3)*

5 Both CFT treatment groups will have the same treatment frequency of seven treatment
6 sessions over 12 weeks plus a 'booster' session at 26 weeks (initial consultation 60 minutes,
7 follow ups 30-40 minutes), in physiotherapy clinics. In both groups, clinicians will use a
8 structured approach to address the relevant cognitive, emotional and behavioural (functional
9 and lifestyle) factors deemed relevant to the individual's presentation¹⁷.

10
11 Based on prior screening (Orebro Musculoskeletal Pain Questionnaire and the Patient-
12 Specific Functional Scale) combined with a comprehensive interview and functional
13 examination, the clinician will identify the multidimensional contributors to pain, distress and
14 disability. This will enable the physiotherapist to design a management plan that is tailored to
15 the person's unique clinical presentation and context.

16

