6 prompt the patient when they ‘break a movement rule’ that has been programmed for them by
7 the clinician. Individualised movement ‘prompts’ may be time-based, such as reducing long
8 periods of sitting without getting up and moving, or may be kinematically-based, such as
9 reducing sitting in an excessively upright position.

10
11 There is no provision for trial-funded ancillary or post-trial care.

12 13 **Clinician recruitment and training**

14 Depending on recruitment and training success, approximately 16 physiotherapists (8 in each
15 city) will deliver the interventions at private physiotherapy clinics. Each physiotherapist will
16 deliver only one CFT treatment arm, to prevent learning (contamination) from experience
17 using the movement sensor output being applied to the CFT-only patients. Physiotherapists
18 will be randomised into either the CFT-only group or CFT-plus-movement-sensor-
19 biofeedback group. Up to four additional physiotherapists will be recruited and trained in
20 each city to act as reserves if required. For physiotherapists to be considered for inclusion in
21 the training program, they will need to have: at least 2 years clinical experience post-
22 graduation; experience treating people with chronic LBP; an interest in applying
23 biopsychosocial management principles via CFT; a willingness to use movement sensors
24 clinically; less than 4 days of prior exposure to CFT training; and a willingness to be

1
2
3 1 observed and videoed for mentoring and feedback purposes while treating a *non-trial* patient
4
5 2 with disabling LBP.
6
7
8 3

9
10 4 The clinician training for both the CFT-only group and CFT-plus-movement-sensor-
11
12 5 biofeedback group will consist of three components: (i) clinical workshops including live
13
14 6 patient demonstrations and mentoring of the physiotherapists while treating patients, (ii)
15
16 7 online resources (e.g. e-book and training videos) and (iii) Facebook private support group
17
18 8 pages.
19
20
21 9

22 23 24 10 *CFT training*

25
26 11 Six clinical workshops will be conducted (a two-day workshop every month for 6 months) in
27
28 12 each city where both CFT-only and CFT-plus-movement-sensor-biofeedback groups will
29
30 13 train together. A final single day workshop will be held for each group separately when
31
32 14 clinicians will need to demonstrate a pre-defined level of competency, as evaluated by the
33

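### The primary model does not adjust for city; if city is prognostic, the gap is charged to therapist variance and the CFT-plus versus CFT-only test loses power

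*Supplement*

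**What the plan says.** All references are to the revised protocol (R1).

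- **Model.** Under Statistical analysis, Treatment efficacy analysis, a repeated-measures linear mixed model is used, with "the primary comparison being a formal test of adjusted mean differences between groups at" 13 weeks. It adjusts for "baseline scores of symptom duration, pain intensity, activity limitation (RMDQ score"), and then for "treatment expectations and significant clinician cluster effects". Secondary outcomes use the equivalent models.
- **Sites.** Methods and analysis states: "The trial will be conducted in Perth and Sydney, Australia". City does not appear among the covariates.
- **Therapists.** Clinician recruitment and training states: "Depending on recruitment and training success, approximately 16 physiotherapists (8 in each" city). Each delivers only one CFT arm, and they are randomised to an arm. Usual-care participants have no trial therapist.
- **Allocation.** Randomisation states: "After completing the baseline assessment, dynamic (adaptive) random allocation will be used", with "Randomisation using a 1:1:1 allocation ratio". No balancing factor is named. The same section says the NHMRC "Clinical Trials Centre will be blinded to baseline assessment".

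**The concern.** Therapist is nested in city. If patients in one city do better than those in the other for reasons the listed covariates do not capture, therapists in that city will have better average outcomes in both CFT arms. A model without city can only read this as therapists differing from one another. Between-therapist variance is the error term for CFT-plus against CFT-only when the clinician term is kept, and that is the contrast named in the sample-size calculation. If therapists and patients are spread evenly over the two arms within each city, the city gap cancels out of the estimated difference, so only its reported standard error grows.

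The rule for keeping the clinician term adds a second route. The term stays only if it is significant, so an unmodelled city gap can decide which primary model is fitted. In usual care there is no therapist term, and nothing in the model captures city.

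**Working it through.** **The plan's own figure.** The sample-size section gives a 2-point difference, SD 6, 5% significance (taken as two-sided), 80% power, 20% dropout and 164 per group. Those inputs need 142 completers per arm, or 142/0.8 = 178 recruited, so 164 is not reproduced. With 164 × 0.8 = 131.2 completers, SE = 6 × √(2/131.2) = 0.741 and power is 77.0%. That is a separate matter, and the point here does not depend on it.

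**Assumed layout.** About 16 therapists over two CFT arms gives 8 per arm. I assume 4 per city in each arm, 16 completers per therapist (8 × 16 = 128 per arm, close to 131), SD 6, no other therapist variance, and a city gap of d points. The documents give no value for d.

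**Therapist-level standard error.**
- Sampling variance of a therapist mean: 36/16 = 2.25.
- Without city, the gap adds 16 × d²/4 = 4d² to the between-therapist sum of squares of means, on 16 − 2 = 14 df. The expected variance of therapist means becomes 2.25 + 4d²/14 = 2.25 + 2d²/7.
- Reported SE of the difference: √[(2/8) × (2.25 + 2d²/7)].
  - d = 0: √0.5625 = 0.75
  - d = 1: √(0.25 × 2.536) = 0.80
  - d = 2: √(0.25 × 3.393) = 0.92
- The true sampling SD of the estimate stays at about 0.75 throughout. With city in the model the reported SE is also about 0.75.

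**Effect on the clinician test.** Its expected F ratio without city is about (16 × 2.536)/36 = 1.13 at d = 1 and (16 × 3.393)/36 = 1.51 at d = 2, against 1 when therapists do not differ.

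**Power under the plan's rule.** I simulated therapist means, kept the clinician term only when its test gave p < 0.05, and otherwise used the patient-level error. The true difference is 2 points.

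| Assumed city gap | Clinician term kept, no city in model | Power without city | Power with city |
|---|---|---|---|
| 0 | 5% | about 74% | about 74% |
| 1 point | 10% | about 72% | about 74% |
| 2 points | 31% | about 62% | about 74% |

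With city in the model, the clinician term is kept in 5% of trials whatever the gap. At a half-point gap the difference in power is negligible (73.0% against 73.3%).

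**Two bounding cases.**
- *Clinician term always kept.* Power without and with city is about 65% and 69% at 1 point, and about 53% and 69% at 2 points. With no gap, adding city costs about half a point (69.9% to 69.4%). If the software holds the therapist variance at zero or above, the figures are 61.5% and 64% at 1 point, and 52% and 64% at 2 points.
- *No clinician term.* City explains R² = d²/(4 × 36) of the variance for an even split, and the SE excess is 1/√(1 − R²) − 1. That is 0.4% at 1 point and 1.4% at 2 points; adjusting would raise power from 77.0% to 77.3% or 78.2%.

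**The case against.** The case against has real weight.

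- **The size of the gap is unsupported.** A 2-point city gap equals the whole target treatment effect, and it would have to remain after adjustment for baseline RMDQ, pain and duration in patients recruited under the same criteria. The simulation includes none of those covariates. This stands: the 2-point row is an upper illustration, and a gap of 1 point or less costs about 2 points of power or fewer.
- **The layout is assumed.** The therapist number is approximate and depends on recruitment, and no stratification of therapists by city is stated. This stands, and the figures are labelled accordingly.
- **City is not documented as an allocation factor.** If it is not one, leaving it out is a choice of covariates and the test remains valid. This stands too, but the nesting of therapists in city gives a reason to include it either way.
- **No separate analysis plan is shown,** and site terms are often settled there. That is fair. The protocol does give an explicit covariate list, though, and city is not on it.

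A reader might also infer that every allocation factor must be missing from the model, because the allocating centre does not see the baseline assessment and expectations are recorded after randomisation. The documents do not support that. No factor is named. Pain intensity and episode duration are eligibility items screened by phone before the online baseline assessment, so they could be allocation factors and are already covariates. The scheme might also balance only the arm totals.

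**Conclusion.** The point holds in conditional form. City is absent from the stated model, and therapists are nested in city. If city is prognostic after the listed covariates, the reported standard error for CFT-plus versus CFT-only is too large, and the choice between models with and without a clinician term can turn on a city gap. There is no bias and no inflated type I error.

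Under the plan's rule and the assumed layout, the power lost is about nil with no gap, about 2 points at a 1-point gap and about 12 points at a 2-point gap. It would be wrong to state as fact that the standard errors are too large, because the documents give no city effect. It would also be wrong to take the drop to 53% as the plan's power: that figure belongs to a clinician term that is always kept. Whether the model omits allocation factors cannot be decided from the documents. This is a cheap improvement to the model; it does not make the planned test invalid.

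**What to change.** Add city (Perth/Sydney) as a fixed effect in the primary and secondary mixed models, and have it in the model before any clinician effect is assessed. State which factors, if any, the dynamic allocation balances on, and add those that are not already covariates.

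The cost is a line or two of analysis wording and one or a few degrees of freedom. City is known for every participant. If city turns out not to be prognostic, the loss is up to about half a point of power. The change should be fixed before group allocation is revealed to the statisticians.
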